The overall hypothesis is that the ropivacaine combined with clonidine administered via single injection ultrasound guided bilateral rectus sheath blocks is a more complete and feasible pain control approach than ropivacaine alone. We will test this hypothesis by pursuing the following specific aims: 1) determine if the ropivacaine/ clonidine combination is superior in providing long-lasting analgesia to ropivacaine alone; and 2) advance the understanding of ropivacaine/ clonidine rectus sheath blockade, and determine if this combination significantly improves satisfaction with pain control due to psychological benefits of clonidine.

We view this innovative study as a first step in developing an evidence-based therapeutic pain regimen for laparoscopic appendectomy. Every hour of effective analgesia counts, as it improves quality of care and reduces health care costs. Upon successful completion of this project, we will seek further support to prospectively validate this combination for other trunk blocks as well as various surgical procedures. The safety of ropivacaine/clonidine blockade should be evaluated in large scale prospective studies.

B. SPECIFIC AIMS AND METHODS TO BE EMPLOYED

Laparoscopic appendectomy is a popular and minimally invasive technique used for removing the appendix, but it is associated with significant pain and anxiety in pediatric populations. The goal of this pilot study is to examine whether ropivacaine/clonidine is effective at prolonging analgesia beyond the effects of ropivacaine alone and to investigate the underlying mechanism (i.e. anxiety reduction) that may make this combination better suited for postoperative pain control, so that better therapeutic regimens can be offered to our patients. The overall hypothesis is that the ropivacaine /clonidine rectus sheath blockade is a more complete and feasible pain control approach after laparoscopic appendectomy. This hypothesis will be tested by the following specific aims:

Aim 1. To determine if the ropivacaine/clonidine combination can prolong analgesia, we will determine if ropivacaine/clonidine rectus sheath blockade is superior in providing long-lasting analgesia compared to ropivacaine alone. Aim 1A will compare duration of paresthesia at the umbilicus instrument site. Aim 1B will compare duration of analgesia at the same location.

The methodology will be the following:

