Aim 1A: On the day of surgery, patients will be asked about paresthesia and loss of sensation around the umbilicus. We will document the time when normal sensation returns following the administration of the block. The time elapsed (in minutes) between rectus sheath blockade and the point at which normal sensation returns will be compared between the groups.

Aim 1B: Every 2 hours, we will question the patients regarding their need for pain medication and obtain their Numeric Rating Scale (NRS) pain scores for umbilicus incisional pain. We will document when the patient needs pain medication. The time elapsed (in minutes) from the rectus sheath blockade until the first request for umbilicus pain medication, as well as NRS pain scores will be compared between groups.

Hypothesis:

We hypothesize that rectus sheath injections with the ropivacaine/clonidine combination will be superior in providing long lasting analgesia compared to ropivacaine alone, increasing the duration of sensory block and analgesia, and lowering pain scores at the umbilicus incision.

Aim 2. We will determine if any improvements we observe in pain control satisfaction with the ropivacaine/clonidine combination can be attributed to clonidine's ability to reduce anxiety.

Aim 2A will compare between the two groups patient, parent, and nurse NRS satisfaction scores and correlate them with post-op scores on the state-anxiety component of the State-Trait Anxiety Inventory for Children (STAIC S – Anxiety). Aim 2B will compare postoperative

STAIC S – Anxiety scores between the two groups. Aim 2C will compare within the two groups the difference between the pre and post- op STAIC S Anxiety scores to show if ropivacaine/clonidine is more effective at reducing anxiety.

The methodology will be the following:

Aim 2A: NRS pain control satisfaction scores from patient, parent and nurse will be collected at the completion of the study. State-Trait Anxiety Inventory for Children (STAIC S – Anxiety) questionnaires will be administered to both groups before surgery, and at hour 6 after rectus sheath injections. Post-op anxiety scores in each group will be correlated with satisfaction scores. Aim 2B: The postoperative STAIC S – Anxiety scores will be compared between the 2 groups. Aim 2C: The pre-op STAIC S Anxiety scores will be compared with post- op STAIC S Anxiety within each group.

Hypothesis:

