To overcome the challenge of developing a blocking agent that has both minimal side effects and duration long enough to outlast the pain, additional substances (epinephrine,

clonidine, dexamethasone, tramadol, buprenorphine, midazolam, dexmedetomidine, and ketamine) have been added to the local anesthetics comprising the nerve blocks. (7) (8) Among the adjuvants, clonidine—an alpha 2 adrenoreceptor agonist—has been shown to prolong the duration of analgesia when administered in the epidural space in children. (9), (10) Clonidine has also been added to local anesthetic for peripheral nerve blocks, but its perineural use is controversial and its exact mechanism of action is unclear; from the limited available data, perineurally administered clonidine appears to be safe, with an efficacy that has yet to be determined. Meta-analyses conducted in adult populations have found that clonidine from 30-300 mcg prolongs the time to the first analgesic request by only 2-2.5 hrs. (11) (12)

The pediatric literature regarding the use of clonidine for peripheral nerve blocks lags behind adult literature and is conflicting. Few small and under-powered studies showed at best a weak trend in favor of clonidine. (13), (14) (15) (16), (17), (18), (19) A retrospective review of 215 patients showed that the use of clonidine in conjunction with local anesthetic is effective in some locations but not others, prolonging analgesia in infraclavicular, lumbar plexus, femoral, fascia iliaca and sciatic nerve blocks by 20-50%. The increased duration of sensory blockade, however, was also associated with an increased the incidence of motor block. (16) No pediatric or adult studies were performed involving trunk blocks such as rectus sheath, transversus abdominis plane, or paravertebral nerve blocks. Side effects reported after neuroaxially or peripherally administered clonidine in conjunction with local anesthetic are hypotension, sedation, fainting, and prolonged motor blockade. (12) (16), (11) (13) Clonidine 1-2 mcg/kg is suggested for use with local anesthetic for single injections peripheral nerve blocks. (20)

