Minimal sedation can be desired for some pediatric patients that underwent surgeries. Clonidine produces effective sedation for patients on mechanical ventilation that can be uncomfortable because anxiety, pain and endotracheal intubation. (21) Clonidine at 2 mcg/kg prevents sevoflurane-induced agitation (22), (23) and can be used as premedication in children. (24), (25) Oral clonidine can relieve postoperative anxiety, and subsequently improve pain control. (26) No studies have investigated its role as an anxiolytic when added to local anesthetic for a nerve block.

Preliminary studies:

The Children's Hospital of Pittsburgh of University of Pittsburgh Medical Center (CHP of UPMC) has a dedicated service that performs peripheral nerve blocks on a regular basis. Over the last academic year, 190 patients (10-17 years old, 126 patients) that underwent laparoscopic appendectomy had peripheral nerve blocks (rectus sheath and transversus abdominis plane). Our experience suggests that children localized the majority of their pain to the umbilicus instrument site. (6) To treat this pain is crucial, as this pain interferes with eating, bedside activities and ambulation, and can delay discharge.

Our preliminary study (retrospective chart of 50 patients that underwent laparoscopic appendectomy) demonstrates that rectus sheath blocks, which target pain at the umbilicus instrument, are as effective as a combination of transversus abdominis plane and rectus sheath blocks, which target pain at all instrument sites. This is an important finding, as it means that instead of dividing the amount of local anesthetic delivered between four sites,

more anesthetic can be delivered bilaterally to a single location. This can result in analgesia that lasts around 12 hours, which is relatively short for our purposes but still an improvement.

[name] prospective study demonstrates that postoperative pain scores after laparoscopic appendectomies correlate very well with postoperative anxiety (Pearson coefficient =0.539;133 subjects, 11-17 years old). Patients that received regional anesthesia for laparoscopic surgeries reported less anxiety after surgery (Spearman coefficient = -0.143, $p = 0.042$; pending publication; 202 subjects, 11-17 years old). The use of single injection nerve blocks predicts less postoperative pain ($p=0.04$), better mood ($p=0.009$), less catastrophizing thoughts about pain ($p=0.007$).

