Descriptive statistics will be presented as frequencies (percentages, %) for categorical data or as mean \pm standard deviation (SD) or median and interquartile range for normally or non-normally distributed continuous data, as appropriate. Examination of normal distribution assumption for continuous data will be determined by q-q plots and histograms. Two sample T-Test or Wilcoxon-Mann-Whitney test will be performed to determine differences between groups for normally or non-normally distributed continuous data, respectively. Pearson's chi-square or Fisher's exact test, as appropriate, will be used to compare the frequency distribution of categorical variables between the groups. We will compute Pearson correlation coefficient between NRS pain scores and the anxiety scores. If the assumptions for the parametric test are not met, a nonparametric alternative will be used (i.e. Spearman correlation coefficient).

Sample Size and Power:

The target sample size was calculated with the assumption that the duration of block in the group with ropivacaine only is 720 minutes \pm 288 minutes and in the group with ropivacaine and clonidine the duration is 1080 minutes \pm 432 minutes. The difference would be clinically relevant if the duration of blocks with ropivacaine and clonidine will be at least 50% or more than the duration of blocks with local anesthetic only. Assuming a power of 80%, a level of significance of 0.05, mean and SD as above, only 12 patients would be required in each group. Allowing for a 400% loss arising from patient dropout, unsuccessful block, incomplete follow up because of discharge home on the day of surgery, and inability to determine when paresthesia wears off, we plan to recruit 50 patients in each group, for a total of 100 patients. We estimate that this sample size of 100 patients would provide 80% power to detect a difference as small as 23% in the duration of paresthesia between these 2 groups.

F. SIGNIFICANCE AND APPLICABILITY

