To our knowledge, this is the first study to investigate if ropivacaine /clonidine rectus sheath blockade is a better and more complete therapeutic regimen for patients undergoing laparoscopic appendectomy. While the patients that underwent uncomplicated laparoscopic appendectomy are treated as inpatients for at least one day, CHP wants to implement early discharge strategies. Unfortunately, the pain after the day of surgery can be significant (3), and causes some parents to be reluctant to have their children discharged. Analgesia advice can be poorly retained (27) and parents can feel overwhelmed about home pain management. Furthermore, some parents believe that using pain medication in childhood may lead to later drug abuse. (28) This is particularly concerning, as parents often undermedicate their child's pain, with up to 60% of parents administering less than the prescribed analgesia on the following day after surgery discharge. (29), (30) A child with long lasting pain control and less anxiety from ropivacaine/clonidine rectus sheath blockade would help the parent better cope with the surgical event, facilitating early discharge.

We would like to mention that patient's satisfaction with pain control is becoming an increasingly important aspect of health care reimbursements reported via the Hospital Assessment of Healthcare Providers and Systems (HCAHPS) survey. The ropivacaine/ clonidine rectus sheath blockade in combination with multimodal therapy can serve as a better therapeutic regimen than the standard of care, improving quality of care, increasing satisfaction and saving health care costs.

G. POTENTIAL LIMITATIONS AND FUTHER DEVELOPMENT

First, although we will record the pain scores and analgesics consumption for pain located at the umbilicus instrument size, our data is subject to some bias. These predictors of analgesia may be prone to misclassification. The visceral/gas pain can be confused with incisional pain, and some patients will need analgesics for another type of pain and location. We believe that using paresthesia as surrogate for analgesia is a better and more complete indicator of duration of analgesia.

Second, preoperative anxiety may reflect in postoperative anxiety scores. However, we believe that comparing preoperative and postoperative anxiety and pain scores will help minimize this bias.

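### Aim 1 asks about analgesia, but the plan prefers numbness as an unvalidated surrogate and has no rule for a result positive for numbness only

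*Combined protocol and SAP*

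**What the plan says.** Section B states that Aim 1 will determine whether the combination "is superior in providing long-lasting analgesia compared to ropivacaine alone". The end of section C repeats long-lasting analgesia as the primary aim. Two outcomes serve it:

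- **1A, numbness:** "Aim 1A will compare duration of paresthesia at the umbilicus instrument site".
- **1B, analgesia:** the time "from the rectus sheath blockade until the first request for umbilicus pain medication, as well as NRS pain scores will be compared between groups".

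The Aim 1 hypothesis names sensory block, analgesia and pain scores together. Neither 1A nor 1B is named as the primary endpoint.

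Section G then discounts the direct measures. Its reason is "The visceral/gas pain can be confused with incisional pain, and some patients will need analgesics for another type of pain and location", and it concludes: "We believe that using paresthesia as surrogate for analgesia is a better and more complete indicator of duration of analgesia".

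Section E sizes the trial on a block duration of 720 min (SD 288) against 1080 min (SD 432). It then says that 100 patients "would provide 80% power to detect a difference as small as 23% in the duration of paresthesia".

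Under Postoperative Study Protocol (section D), assessments run every 2 hours until numbness resolves or the child goes home. Under Patient eligibility, children discharged before numbness resolves are left out of the Aim 1 analysis.

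**The concern.** The question is how long pain relief lasts. The outcome that drives the sample size, and that section G says to trust, is how long the skin stays numb. These can differ, because both arms receive ketorolac (unless contraindicated) and acetaminophen every 6 hours for 24 hours, so a child may regain sensation and still need nothing more.

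If 1A is positive and 1B is not, the plan does not say what the trial concludes. Section G offers a ready argument for concluding longer analgesia anyway. The main claim would then rest on an assumption that the trial neither supports with data nor plans to check.

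**Working it through.** **1. Which quantity do the planning values describe?**

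| Place | Figure | Described as |
|---|---|---|
| C, Preliminary studies | about 12 h without clonidine | analgesia: "This can result in analgesia that lasts around 12 hours" |
| C, Preliminary studies | 18-22 h with clonidine | paresthesia and analgesia, one range for both |
| E, Sample Size and Power | 720 and 1080 min | duration of block |
| E, Sample Size and Power | 23% detectable | duration of paresthesia |

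12 h × 60 = 720 min and 18 h × 60 = 1080 min. So the control value matches a figure given for analgesia, while the detectable difference is stated for numbness.

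**2. The plan's own figures.** With SD 288 in both arms, two-sided 0.05 and 80% power, n = 2 × (1.96 + 0.842)² × 288² / 360² = 10.05, so 11 per arm by the normal approximation. The t-based value is 11.09, rounded up to the stated 12. At 50 per arm the detectable difference is 2.802 × 288 × √(2/50) = 161.4 min, and 161.4/720 = 22.4% (22.6% with t), in line with the stated 23%. Using both stated SDs, the requirement is 17 (normal) or 18 (Welch) per arm, which 50 recruited can still cover. No calculation is given for time to first request.

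**3. Power of 1B for the gain that the plan cites.** Section C reports that, in adults, clonidine "prolongs the time to the first analgesic request by only 2-2.5 hrs", that is 120-150 min. As shares of this trial's planning values, 120/720 = 17% and 150/720 = 21% of the control mean, and 120/360 = 33% and 150/360 = 42% of the assumed gain. The adult baseline is not given, so the first pair of percentages is only a scale.

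The documents give no SD for time to first request. Assume the block-duration SDs, a two-sided t-type test at 0.05 and no censoring. The standard error at 50 per arm is √((288² + 432²)/50) = 73.4 min, or √(2 × 288²/50) = 57.6 min with SD 288 in both arms.

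| 50 per arm | SDs 288 and 432 | SD 288 in both |
|---|---|---|
| 1B, gain 120 min | 37% | 54% |
| 1B, gain 150 min | 52% | 73% |

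For 80% power, 1B would need 58-91 per arm (SD 288) or 95-147 per arm (root-mean-square SD 367). In contrast, 1A at its assumed 360 min has 99.8% power at 50 per arm with SDs 288 and 432. Disagreement between the two tests is therefore a realistic outcome that the plan should provide for.

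**4. Can 1B act as the direct check as planned?** Take two children who would each first ask for umbilical analgesia at 900 min. In one, numbness ends at 720 min and assessments stop, so the request falls outside the planned record. In the other, numbness ends at 1080 min and the request is recorded. Request times are identical, yet only the child with longer numbness contributes the late one. With no true effect on request time, the mean of recorded times would therefore tend to be longer in the arm with longer numbness. The size depends on distributions that the documents do not give.

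The Aim 1 exclusion works the same way: still being numb at discharge removes a child from 1B as well as from 1A. Section E plans only t or Wilcoxon-Mann-Whitney tests for continuous data, with no provision for children who have not made a request.

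**The case against.** The strongest reply is that the plan already keeps the outcomes apart. Section B labels 1A paresthesia and 1B analgesia, the hypothesis requires both, and a null 1B would be visible. The surrogate sentence is one opinion in a limitations section, it comes with a reason, and this is a self-described pilot. All of that is fair. But the reason explains distrust of pain reports. It does not show that numbness tracks analgesia, and visibility of 1B is not a rule for interpreting it.

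Three stronger readings are tempting and are not supported:

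- *A reader might infer that a positive 1A will be reported as longer analgesia.* No text says that 1A alone suffices; the plan only leaves this open.
- *A reader might infer from the cited evidence that analgesia will hardly lengthen.* Section C is mixed. Besides the adult 2-2.5 h and at best a weak trend in small pediatric studies, it cites a pediatric review with 20-50% longer analgesia in some blocks (144-360 min on a base of 720). The team's own experience is that both outcomes lengthened. Nothing cited shows numbness lengthening without analgesia. The 50% relevance threshold is also defined for block duration, not for request time.
- *A reader might take the chance of a positive 1A with a negative 1B as the rate of false analgesia claims.* The power figures above assume a true gain of 120-150 min, so a missed 1B there is a false negative. They show that 1B has limited power, not how often the surrogate misleads.

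**Conclusion.** The point holds as a gap in the rules for concluding. The surrogate is argued but not validated, the sample size rests on block or paresthesia duration, and Aim 1 has neither a primary endpoint nor a rule for discordant results. A numbness-only finding could be presented as longer analgesia. This follows from the text and needs no assumption about the drug's effect.

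The risk of a false analgesia claim cannot be quantified from the documents. What can be sized is the direct measure's power: about 37-73% at 50 per arm for a 120-150 min gain, if request times have SDs like those assumed for block duration. It would be lower with fewer evaluable children. Separately, 1B as now observed depends on 1A, and this must be corrected before 1B can carry the analgesia claim.

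**What to change.** 1. **Section G:** replace the surrogate sentence. Say that numbness measures sensory block and that its relation to analgesia is not established.
2. **Section B, Aim 1:** state that a result positive only for 1A is reported as longer duration of sensory block. Any claim of longer analgesia rests on 1B: time to first umbilical analgesic request, with NRS pain scores as support.
3. **Section D:** record the first umbilical request over a fixed window that does not depend on numbness, for example the 24 hours of the postoperative regimen. Keep children discharged while numb in the 1B analysis.
4. **Section E:** compare 1B with a time-to-event method, censoring children with no request at the end of their observation. Report how many are censored at discharge, by arm, since that censoring may not be neutral.
5. **Section E, Sample Size and Power:** label 720 and 1080 min as numbness or analgesia times.

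**Cost.** Items 1, 2 and 5 are wording. Items 3 and 4 need some recording after numbness resolves and a revised analysis paragraph; a table of the gap between end of numbness and first request could not be built from the planned assessments alone. A numbness-only result can no longer be called longer analgesia, and given 1B's limited power a true but modest analgesic gain may go unclaimed. The plan should say so.

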In the operating room, standard anesthesia monitors will be connected and general anesthesia will be performed as per the anesthesiologist's standard of care. At the completion of surgery, acetaminophen iv and ketorolac will be administered by the anesthesia provider. Dexmedetomidine will not be administered during anesthesia or after the completion of anesthesia. A member of CHP Acute Interventional Perioperative Pain Service (AIPPS) – attending or fellow will perform all bilateral ultrasound guided rectus sheath blocks as per CHP standard of care using the study drug. The surgeon will not infiltrate the local anesthetic at the laparoscopic instrument sites.

Postoperative Study Protocol:

For the following 24 hours, the analgesic regimen will include ketorolac every 6 hours (if not contraindicated by surgeon), acetaminophen iv every 6 hours, oxycodone by mouth as needed for pain, every 4 hours, and hydromorphone iv as needed for pain, every 2 hour.

In the postoperative period the patients will be asked to complete a few questionnaires created for this study. The nurse taking care of the patient, principal investigator, one of the co-investigators, or the research assistant will do the assessment. Starting in the PACU, the patients will be questioned about the presence of paresthesia around the umbilicus instrument site ("is the area around your belly button numb") and the umbilical pain severity using NRS scale (0 being no pain and 10 the worst imaginable pain). They will also be asked about their need for pain medication for umbilical pain as well as the amount of pain medication they have consumed for pain in that region. The assessment will continue on the floor every 2 hours until complete resolution of paresthesia at the umbilicus or until the patient is discharged home. The state version (S-anxiety) of the State-Trait Anxiety Inventory for Children (STAIC) will be administered to measure patient anxiety before surgery after the consent is done and 6 hours after rectus sheath injections. At the completion of the study,

the patient's, parent's, and nurse's satisfaction with pain control will be investigated using an NRS scale (0 being very unsatisfied and 10 being very satisfied).

E. STATISTICS: ASSESSMENT OF ADEQUACY OF SAMPLE SIZE

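### The limitations section relies on comparing anxiety and pain before and after surgery, but no preoperative pain score is scheduled and the preoperative STAIC is not used in the between-group anxiety comparison

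*Combined protocol and SAP*

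**What the plan says.** Section G (potential limitations) raises the concern that "preoperative anxiety may reflect in postoperative anxiety scores" and replies that "we believe that comparing preoperative and postoperative anxiety and pain scores will help minimize this bias".

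The assessments are set out in section D, Postoperative Study Protocol:

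- **Pain.** "Starting in the PACU, the patients will be questioned about the presence of paresthesia around the umbilicus instrument site". The same sentence adds the 0-10 umbilical pain score. Then: "The assessment will continue on the floor every 2 hours until complete resolution of paresthesia at the umbilicus", or until discharge if that comes first. Aim 1B in section B says that staff will "obtain their Numeric Rating Scale (NRS) pain scores for umbilicus incisional pain" and compare the scores between groups.
- **Anxiety.** The state scale of the STAIC "will be administered to measure patient anxiety before surgery after the consent is done and 6 hours after rectus sheath injections".

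The analyses are in sections B and E. Aim 2B compares postoperative STAIC scores between the two groups. Aim 2C uses the preoperative score: "The pre-op STAIC S Anxiety scores will be compared with post- op STAIC S Anxiety within each group". Section E offers t or Wilcoxon-Mann-Whitney tests for continuous outcomes, chi-square or Fisher tests for categorical ones, and a correlation of NRS pain with anxiety. It names no model with a baseline covariate.

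**The concern.** A limitations section that names a bias and a remedy tells the reader that the remedy can be carried out. Here, one of the two scores to be compared before and after surgery is never taken before surgery. The other is taken, but it is left out of the analysis where it would help most.

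The second part matters more. Aim 2 asks whether clonidine reduces anxiety, and the comparison that answers this is between the arms. If children differ in anxiety before surgery and this persists, the preoperative STAIC should enter that comparison. Two separate within-group comparisons do not do the job: each arm can change, or fail to change, without this showing that the arms differ.

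At stake are the precision of Aim 2B, a description of how alike the arms were in pain before treatment, and the accuracy of a claim that would probably be repeated in the report.

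**Working it through.** No figure in the plan needs reproducing. The check sets the schedule and the analyses beside the claim.

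**1. What is measured, and when (sections B and D).**

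- STAIC S-Anxiety: 1 assessment before surgery, 1 after (hour 6 after the block).
- Umbilical NRS pain: 0 before surgery; after it, in the PACU and then every 2 hours.
- Satisfaction: 0 before surgery, 1 at the end of the study.

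A comparison of before with after is therefore possible for anxiety and impossible for pain. The study period starts at consent (Study Duration), so a preoperative window exists, but no pain score is placed in it.

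**2. How the preoperative score is used (sections B and E).**

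- Aim 1B: postoperative pain and time to first request, between groups. No baseline.
- Aim 2A: satisfaction between groups, correlated with postoperative anxiety. No baseline.
- Aim 2B: postoperative anxiety between groups. No baseline.
- Aim 2C: preoperative against postoperative anxiety, within each group. This is the only use of the baseline.

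**3. What leaving the baseline out of Aim 2B does.** Let d be the chance difference between arms in mean preoperative STAIC, and ρ the within-arm correlation of preoperative with postoperative STAIC. With equal SDs before and after, the unadjusted postoperative difference has expectation

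treatment effect + ρ × d.

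Randomization makes the average of d zero, so there is no bias. In any one trial, d has standard error √(2/n) in SD units:

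- n = 50 per group (the recruitment target): √(2/50) = 0.20 SD.
- n = 12 per group (the number section E says is required before allowing for losses): √(2/12) = 0.41 SD.

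So a typical baseline imbalance would move the Aim 2B difference by about 0.20ρ SD with full retention, and by up to 0.41ρ SD if losses used up the whole allowance. The second case is an extreme for Aim 2, since children discharged before paresthesia resolves are dropped from the first aim only. ANCOVA removes the ρ × d term and multiplies the residual variance by about (1 − ρ²). The documents do not give ρ. At ρ = 0 nothing is gained, and the gain grows as ρ rises.

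**4. Why pain cannot be handled in the same way.** The Aim 1B outcome is pain from the umbilical incision, which does not exist before the incision is made. A preoperative score would measure another pain, presumably that of the appendicitis. Subtracting one from the other would have no clear meaning. A preoperative pain item can serve only as a covariate, and it must be defined separately.

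**The case against.** The strongest reply has four parts.

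- **The bias named is carry-over of anxiety, and its baseline is collected.** This is correct, and it limits the point. Baseline pain is not needed to compare anxiety before and after surgery. But collecting the baseline does not bring it into Aim 2B.
- **The sentence can be read differently.** It may mean anxiety before and after, together with pain scores, as in the correlation planned in section E. The plain grammar applies both time points to both scores. If the narrower sense was meant, the sentence still needs rewording.
- **No endpoint or test rests on the phrase.** This is true. Aim 1A and the sample size rest on block duration, and section E plans no analysis of pain before against after.
- **The aim statement for 2C could be taken as a between-group comparison of change**, since its purpose is to show that the combination reduces anxiety more. The methodology for that aim says the comparison is made within each group, and section E names no test of change between arms.

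A reader might go further and infer that the missing baseline biases the pain comparison in Aim 1B. The documents do not support that. Allocation is random and blinded, so a between-group comparison is valid without a baseline. The exclusions after allocation, such as a need for patient-controlled opioids, can weaken that protection. They are a separate matter, and a baseline score would describe the resulting imbalance without curing it.

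**Conclusion.** The point holds in a limited form. The safeguard in section G is only partly deliverable: there is no preoperative pain score for any patient, and the preoperative STAIC is absent from the one randomized comparison of postoperative anxiety. The consequence is lost precision in Aim 2B and an overstated claim, not bias. Aim 1A is unaffected.

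The loss of precision cannot be given as a figure, because it depends on ρ for the STAIC, which the documents do not report. A reader might be tempted to size the benefit of a baseline pain score from the correlation between pain and anxiety in the preliminary studies. That correlation relates two postoperative measures, so it says nothing about how preoperative pain predicts incisional pain, and that relation could be close to nil. Nor would the gain from a pain item simply add to the gain from the STAIC if both were in the model.

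The conclusion on the schedule rests on the text alone. The conclusion on precision assumes a roughly linear relation between preoperative and postoperative STAIC. The changes are worth making because they cost almost nothing.

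**What to change.** 1. **Section E and Aim 2B.** State that postoperative STAIC S-Anxiety will be compared between groups by ANCOVA with preoperative STAIC S-Anxiety as covariate, reporting the adjusted difference with its 95% confidence interval. Aim 2C can stay as description. This uses data already collected and costs one sentence.
2. **Pain: choose one.**
   - Add one preoperative item to section D at the existing STAIC contact, after consent and before surgery, in both arms. Define it separately from the postoperative item (for example, current abdominal pain, 0-10). State in section E that it is a covariate for the NRS pain comparison and will not be used to form a change score. The cost is one spoken question and a small amendment to the questionnaire. It has to be in place before patients are enrolled, because the score cannot be reliably recovered after surgery.
   - Or remove the reference to pain from the sentence in section G. This costs nothing and resolves the contradiction, but gives no information on pain before surgery.
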